### **Adverse reaction (ADR)**

An adverse reaction is defined as a response to a medicinal product which is noxious and unintended. Response in this context means that a causal relationship between a medical product and an adverse event is at least a reasonable possibility. Adverse reactions may arise from use of the product within or outside the terms of the marketing authorization or from occupational exposure. Conditions of use outside the marketing authorization include off-label use, overdose, misuse, abuse and medication errors.

### **Serious adverse event**

A serious adverse event is defined as any AE which

- results in death,
- is life-threatening,
- requires in-patient hospitalization, or
- prolongation of existing hospitalization,
- results in persistent or significant disability or incapacity, or
- is a congenital anomaly/birth defect

Life-threatening in this context refers to a reaction in which the patient was at risk of death at the time of the reaction; it does not refer to a reaction that hypothetically might have caused death if more severe.

Medical and scientific judgement should be exercised in deciding whether other situations should be considered serious reactions, such as important medical events that might not be immediately life threatening or result in death or hospitalization, but might jeopardize the patient or might require intervention to prevent one of the other outcomes listed above. Examples of such events are intensive treatment in an emergency room or at home for allergic bronchospasm, blood dyscrasias or convulsions that do not result in hospitalization or development of dependency or abuse. Any suspected transmission via a medicinal product of an infectious agent is also considered a serious adverse reaction.

## **1.2 ADVERSE EVENT AND SERIOUS ADVERSE EVENT COLLECTION AND REPORTING**

INSTITUTION/Investigator will be responsible for reporting AEs which occur during the conduct of the Study to the competent regulatory authorities, accredited Institutional Review Boards and/or Independent Ethics Committee(s) ("IRB/IEC(s)") in accordance with the applicable laws and regulations.

### **1.3 ADVERSE EVENT REPORTING TO BOEHRINGER-INGELHEIM (BI)**

**Dabigatran is not part of the protocol but the following section is added at the request of the sponsor in case patients receive dabigatran.**

INSTITUTION shall report

- (i) all ADRs, serious and non-serious
- (ii) all fatal AEs
- (iii) pregnancies in female subjects and partners of male subjects

which are associated with dabigatran by fax the BI Unique Entry Point ([contact]) using BI NIS SAE report form in following timelines.

All Serious ADRs and AEs with fatal outcome shall be forwarded immediately (within twenty four (24) hours or next business day whichever is shorter).

All non-serious ADRs shall be forwarded within seven (7) days

The investigator carefully assesses whether an AE constitutes an ADR using the information below.

Causal relationship of adverse event

The definition of an adverse reaction implies at least a reasonable possibility of a causal relationship between a suspected medicinal product and an adverse event. An adverse reaction, in contrast to an adverse event, is characterized by the fact that a causal relationship between a medicinal product and an occurrence is suspected.

Medical judgment should be used to determine the relationship, considering all relevant factors, including pattern of reaction, temporal relationship, de-challenge or re-challenge, confounding factors such as concomitant medication, concomitant diseases and relevant history.

Reporting of related Adverse Events associated with any other BI drug

The investigator is encouraged to report all adverse events related to any BI drug other than dabigatran according to the local regulatory requirements for spontaneous AE reporting at the investigator's discretion by using the locally established routes and AE report forms.

## **I. Regulatory Considerations**

## 1. Institutional Review Board (IRB)

Written informed consent will be obtained from study participants at each of the two performance sites. All study personnel will be trained in Good Clinical Practices (GCP) and fulfill other requirements of the University of Miami and Miami VA Hospital Research Committees.

## 2. Subject confidentiality

In order to maintain participant confidentiality, any records that leave the center will be identified only by the Study Identification number (SID). All records will be kept in a locked file cabinet. All computer entry will be done using SIDs only. Clinical information will not be released without the written permission of the participant. The patient contact information and restricted clinical information will be maintained by the study coordinator in a password-protected file on a laptop computer which will be kept in a locked office (CRB 1362).

## 3. Study Registration

The study will be registered at [www.clinicaltrials.gov](http://www.clinicaltrials.gov) prior to initiation.

## 4. Study Modification/Discontinuation

The study may be discontinued at any time by the sponsor as per the contract.

## **J. Future Directions**

In order to have the greatest impact on stroke prevention, it is important to have AF patients on the most effective antithrombotic medication. Furthermore, it is important to have the anticoagulant medication started before a stroke to avoid permanent neurologic injury. Screening high risk patients for AF is one method to identify AF patients prior to the development of a disabling stroke.

We feel that the group of patients with OSA represents an excellent target population for AF screening due to their high frequency of multiple stroke risk factors (hypertension, diabetes mellitus, obesity, etc.). If we are able to establish that the frequency of AF in this population is at least 5%, then a larger study can be justified. Screening of OSA patients would also be a novel method for early identification of individual patients at elevated risk for ischemic stroke. Future studies could also investigate genetic polymorphisms which are associated with an increased propensity for AF. By combining genetic predisposition with environmental factors and conventional risk factors, an “AF prediction” score could be developed for patients with OSA and other conditions such as congestive heart failure.

## **K. Publication Plan**

Our study team is multidisciplinary, including representatives from neurology, cardiology, and pulmonary/sleep medicine. It is likely that this study will be of interest to multiple audiences. Therefore, we would like to target abstract presentations for meetings such as the American College of Cardiology conference, American Academy of Neurology conference, and the meeting of the Associated Professional Sleep Societies.

Journals targeted for publication include the *Journal of the American College of Cardiology* (JACC), *Neurology*, and *Sleep*.

## APPENDIX ONE

Visit schedule and tasks for completion

Time	Tasks for completion
Baseline evaluation	

• CHADS score calculation*

• Obtain informed consent

• Arrange cardiac monitor for patient

• Explain plan for outpatient follow-up

• Complete baseline data collection form

• Heart monitor will be placed

1 week	

• Contact subject to verify that they are wearing the cardiac monitor.

• Ask subject about any adverse events.

• Remind subject to return the heart monitor (in person or via USPS or UPS)

• Schedule 6-month phone call follow-up. This phone call will serve as the study close-out visit.

6 months	Contact subject for study close-out visit

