#### **Description of cardiac monitoring device**

The Lifestar ACT MCT monitor is a continuous ECG monitor and arrhythmia detector that is designed for self-testing by patients at home and for analysis by medical professionals at a remote Monitoring Center. The chest-worn sensor is utilized for the acquisition, recording, and transmission of the ECG signal. The device is equipped with four electrodes on a harness and it houses a 3.6V AA battery, a Bluetooth transceiver and a buzzer. Patients will be monitored over a 2 week of period.

The ECG signals are transmitted via Bluetooth to a handheld device with a proprietary interactive application, arranged to process and transmit the ECG recordings. The handheld device is mobile computing device with a display and a touch input such as a cell phone. It has adequate memory and processing capability to run the proprietary application. This device is already used for routine clinical care at both the University of Miami Hospital and the Miami VA Hospital. A patient quick start guide is attached as an appendix.

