#### **Outcome Measures**

After completion of the four week cardiac event monitor, we will record the frequency of abnormalities such as:

1. Frequent premature atrial contractions
2. Frequent ventricular premature contractions
3. Definite AF (defined as an irregularly irregular rhythm with absence of p waves)
4. Longest duration of AF
5. AF episodes lasting more than six minutes

Initial interpretation of the cardiac monitor is provided by Lifewatch technicians and the reports will be confirmed by the study assigned cardiologist. The Lifewatch technicians receive ECG information only and no identifiable information. We will follow patients for six months after the placement of the cardiac event monitor. We will document selection of antithrombotic therapy including the following:

1. Novel oral anticoagulant (NOAC)
2. Warfarin
3. Antiplatelet therapy
4. No antithrombotic therapy

After all patients have completed the six month follow-up period, we will record the following:

1. Frequency of undetected AF
2. AF frequency according to baseline CHADS score
3. Rate of utilization of anticoagulants in patients with AF
4. Rate of utilization of antiplatelet therapy in patients with AF
5. Predictors of AF based on baseline variables (age, sex, history of CHF, BMI, etc.)

If we find that >5% of patients with OSA and CHADS score of  $\geq 2$  have undetected AF, then this would support a larger multi-center study of screening OSA patients for AF and identifying predictors of AF in this population.

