#### *Risk/benefit considerations*

No benefit can be guaranteed to study participants. However, if they do have early detection of AF, they can be placed on appropriate antithrombotic treatment to prevent stroke, which is a potential benefit.

There are no major risks with the device. Some patients may have skin irritation and special "sensitive skin" leads are available for these patients. There is no restriction with the use of the device with pacemakers or other implanted devices since only surface recordings are made.

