#### **H. Adverse Events**

### **MANAGEMENT AND REPORTING OF ADVERSE EVENTS/ADVERSE REACTIONS**

#### **1.1 DEFINITIONS OF ADVERSE EVENTS**

Adverse event

An adverse event (AE) is defined as any untoward medical occurrence in a patient or clinical investigation subject administered a medicinal product and which does not necessarily have a causal relationship with this treatment. An adverse event can therefore be any unfavorable and unintended sign (e.g. an abnormal laboratory finding), symptom, or disease temporally associated with the use of a medicinal product, whether or not considered related to the medicinal product.

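### The schedule asks about adverse events only at week 1, before monitor wear ends, and not at the six-month call, although the reporting duties run throughout the study

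*Combined protocol and SAP*

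**What the plan says.** Appendix One lists a baseline evaluation, a one-week contact and a six-month contact. The one-week row includes "Ask subject about any adverse events". The whole of the six-month row is "Contact subject for study close-out visit", which the one-week row describes as a telephone call. The monitor may be handed back in person or sent by post or courier.

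Two lengths of wear are stated. The device description says "Patients will be monitored over a 2 week of period", and the Methods section agrees. Outcome Measures says "After completion of the four week cardiac event monitor", and Sample Size Considerations also refers to four weeks. Outcome Measures then says "We will follow patients for six months after the placement of the cardiac event monitor".

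Section 1.2 makes the institution and investigator responsible for reporting adverse events that arise while the study is being conducted. Section 1.3 applies if a participant receives dabigatran, which it says is not part of the protocol. It asks for all adverse reactions, fatal events and pregnancies associated with that drug: "All Serious ADRs and AEs with fatal outcome shall be forwarded immediately", within 24 hours or the next business day, and non-serious reactions within seven days.

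Section 1.1 defines an adverse event as an occurrence "in a patient or clinical investigation subject administered a medicinal product". The Drug Supply Request is none, and the one device effect named under Risk/benefit considerations is "Some patients may have skin irritation".

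**The concern.** The duty to report spans the study, while scheduled asking stops at day 7. Three kinds of event have no scheduled question: device effects in the later part of wear, anything in the remaining months of follow-up, and reactions to an anticoagulant started after AF is found. A low count of recorded events could then mean that nobody asked, and the reader could not tell this from good tolerability.

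The definition adds a second gap. Read literally, skin irritation in a participant who was given no drug is not an adverse event. Because a serious adverse event is defined as a kind of adverse event, the same limit passes to serious events.

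**Working it through.** The plan gives no adverse-event rate and no capture rate, so it has no figure of its own to reproduce here. What can be checked is the coverage of the one scheduled question.

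**Inputs.** Question at day 7 (Appendix One). Wear of 14 days (Methods, device description) or 28 days (Outcome Measures, Sample Size Considerations). Follow-up of six months from monitor placement, taken as 182 days. N = 200 and AF frequency 5% (Sample Size Considerations).

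**Days covered**
- Two-week wear: 7/14 = 50%.
- Four-week wear: 7/28 = 25%.
- Follow-up: 7/182 = 3.8%, leaving 175 days.

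**Share of events after day 7.** These are calendar days, not events. To convert them, assume the event rate in week 1 is *m* times the later rate. Over a period of *D* days the share after day 7 is (D − 7)/(7m + D − 7).

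| m (assumed) | 14-day wear | 28-day wear | 182-day follow-up |
|---|---|---|---|
| 1 | 7/14 = 50% | 21/28 = 75% | 175/182 = 96% |
| 5 | 7/42 = 17% | 21/56 = 38% | 175/210 = 83% |
| 10 | 7/77 = 9% | 21/91 = 23% | 175/245 = 71% |

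For follow-up as a whole, the share falls to one half only when 7m = 175, that is m = 25. So most events over six months would arise after week 1 unless they are very strongly concentrated in that week. For device effects the conclusion is weaker: if skin reactions come early, only a minority fall after day 7.

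**Anticoagulant exposure.** Expected AF-positive patients: 200 × 0.05 = 10. Only some of them would receive dabigatran, so AF-triggered exposure to it is expected in no more than about 10. Even a patient who started on the day of monitor placement and continued to close-out would have at most 7 of 182 days (3.8%) of exposure before the question. Later starters have less or none.

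**Other routes to the information.** The Data Management Plan says data come from participants by visit or telephone and from the electronic medical record, but it describes record review for cardiac encounters. That route is not designed to find skin reactions or non-cardiac bleeding. Appendix One lists no contact between week 1 and month 6.

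**The case against.** The strongest reply is that Appendix One is not an exhaustive task list. Antithrombotic use has to be recorded over six months, yet the six-month row omits that too, so its silence on adverse events is weak evidence that nobody will ask. Section E points to a Table 1 that is not in the text available; it may be Appendix One itself, or it may hold further items. This stands as a caution. But the one-week row does spell the task out, staff work from the schedule, and any separate table would need to agree with it.

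A reader might infer that the question comes before any AF-triggered drug could be started. The documents do not support that. The ECG is transmitted during wear for remote analysis, and nothing delays the result until wear ends, so detection and a prescription within week 1 are possible.

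A reader might also infer that most events would be missed. Having no scheduled question is not the same as being missed. Participants are under the care of co-investigator sleep physicians, leads for sensitive skin are offered, and spontaneous reports and the record may capture some events.

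Nor can a biased safety analysis be claimed. Outcome Measures names no safety endpoint, and none of the stated AF or treatment outcomes is affected. The dabigatran duty is conditional and concerns few patients.

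It is also fair to say that an event outside the Section 1.1 definition is not one the plan has promised to report. That is a reason to correct the definition together with the schedule.

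**Conclusion.** The gap between schedule and duty is real and worth closing. One adverse-event question, at week 1, covers 50% or 25% of wear, depending on which stated length applies, and 3.8% of follow-up. The six-month call has no such item, and the definition does not clearly include the device effect that the protocol itself names.

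The number of events that would go unrecorded cannot be given, because the documents state neither an event rate nor a capture rate. That most follow-up events fall after week 1 is an inference. It holds unless the week-1 rate is about 25 times the later rate or more. The figure of about 10 AF-positive patients rests on the plan's 5% hypothesis.

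It would also go too far to say that the Section 1.3 timelines cannot be met. The text does not say whether they run from the event or from awareness of it. If from awareness, the present schedule does not breach them; if from the event, a question at six months would not satisfy them either. The supportable statement is that the scheduled contacts do not provide for prompt detection after week 1.

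**What to change.** 1. **Appendix One, six months:** add *ask about adverse events since last contact* to the existing call.
2. **Appendix One, monitor return:** collect events up to the end of wear, by asking when the monitor is handed back or by a short form in the mailed return package. A mailed return is not a contact, so the form is needed.
3. **Appendix One, one week:** tell participants to report later events promptly and whom to tell. The six-month question improves completeness but does not by itself support the 24-hour and seven-day timelines.
4. **Section 1.1:** reword the definition to cover any untoward medical occurrence in a participant during monitoring and follow-up, whether or not a medicinal product was given, so that device skin reactions count.
5. **Consistency:** align Table 1 with Appendix One if they are separate, and reconcile the two-week and four-week statements so that the end of wear is a defined date.

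With items 1 and 2, the days covered by a scheduled enquiry rise from 7 of 182 to 182 of 182. No visit is added. The cost is a return form, a few minutes per participant and more events to log. Recall of mild events at six months will be imperfect, which is why items 2 and 3 are needed as well. Sample size, power and the AF outcomes do not change.
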